2.1.3 Secondary endpoint

The occurrence of treatment-emergent AEs.

[figure not shown]
The occurrence of drug-related AEs.

[figure not shown]
2.2.2.1 Safety and tolerability

Safety and tolerability of Spesolimab will be assessed based on:

- Safety laboratory parameters
- 12-lead ECG
- Vital signs (blood pressure [BP], pulse rate [PR], respiratory rate [RR], body temperature)
- Immunogenicity (ADA)

Proprietary confidential information © 2021 Boehringer Ingelheim International GmbH or one or more of its affiliated companies

3. DESCRIPTION OF DESIGN AND TRIAL POPULATION

3.1 OVERALL TRIAL DESIGN AND PLAN

This single-doses and parallel-group design for IV and SC administration trial is designed as open label, within dose groups.

It is planned to include up to 60 healthy male and female subjects in the trial. The subjects will be assigned to 5 groups each consisting of 10 subjects with at least 3 subjects for each gender within each dose group; In case of subjects not completed the trial, up to 10 replacement will be recruited for whole study. The cohorts within each SC and IV dose groups will be dosed sequentially (see Table 3.1: 1).

Only one dose is tested within each dose group. The dose groups to be evaluated are outlined in Table 3.1: 1.

Table 3.1: 1 Dose groups

Dose group	1	2	3	4	5
Dose	IV			SC	
	450 mg	900mg	1200 mg	300 mg	600 mg
No. of subjects entered	10	10	10	10	10
No. of subjects receiving active	10	10	10	10	10

The investigator is allowed to interrupt further dose escalation in the event the safety evaluation leads to concerns until alignment with sponsor is achieved.

The cohorts will be dosed consecutively in ascending order within IV and SC dose groups, and a time interval of at least two weeks will be maintained between the first drug administration to subjects in the previous dose group and the first drug administration to subjects in the subsequent dose group. The decision to treat the next dose cohort will be based upon safety.

An overview of all relevant trial activities is provided in the [Flow Chart](#). For visit schedules and details of trial procedures at selected visits, refer to [sections 6.1](#) and [6.2](#), respectively.

3.2 DISCUSSION OF TRIAL DESIGN, INCLUDING THE CHOICE OF CONTROL GROUPS

The trial will be conducted in an open-label fashion. Blinding is not possible because the treatments are distinguishable. The open-label treatment is not expected to cause bias results, since the pharmacokinetic endpoints are derived from measurement of plasma concentrations of the analyte.

Proprietary confidential information © 2021 Boehringer Ingelheim International GmbH or one or more of its affiliated companies

For safety reasons, a time interval of at least two weeks (taking into consideration that the $t_{1/2}$ of Spesolimab is four weeks) will be maintained between the first drug administration in the previous dose group and the first drug administration of the subsequent dose group within each SC and IV dose groups.

3.3 SELECTION OF TRIAL POPULATION

It is planned that up to 60 including 10 replaced healthy male and female subjects (at least three of each sex within each dose group) will enter the trial. Subjects will be recruited from the subjects' pool of the trial site.

A log of all subjects enrolled into the trial (i.e. who have signed informed consent) will be maintained in the ISF irrespective of whether they have been treated with investigational drug or not.

3.3.1 Main diagnosis for trial entry

The trial will be performed in healthy subjects.

3.3.2 Inclusion criteria

Subjects will only be included in the trial if they meet the following criteria:

1. Healthy male or female subjects (at least three subjects for each gender within each dose group) according to the assessment of the investigator, as based on a complete medical history including a physical examination, vital signs (BP, PR, RR, body temperature), 12-lead ECG, and clinical laboratory tests.
2. Chinese ethnicity, according to the following criteria:
Ethnic Chinese, born in China and have 4 ethnic grandparents who were all born in China.
3. Age of 18 to 45 years (inclusive).
4. Body weight ≥ 50 kg for male and ≥ 45 kg for female with body mass index (BMI) range ≥ 19 and < 26 kg/m^2 at visit 1.
5. Signed and dated written informed consent prior to admission to the trial, in accordance with GCP and local legislation.
6. Female subjects who meet any of the following criteria from at least 30 days before the first administration of trial medication until 16 weeks after trial completion [[c03320877](#)]:
 - Women of childbearing potential (WOCBP)¹ must be ready and able to use highly effective methods of birth control per ICH M3 (R2) that result in a low failure rate of less than 1% per year when used consistently and correctly. A list of contraception methods meeting these criteria is provided in the subject information
 - A vasectomised sexual partner (vasectomy at least one year prior to enrolment)
 - Surgically sterilised (including hysterectomy)
 - Postmenopausal, defined as at least one year of spontaneous amenorrhoea (in questionable cases a blood sample with simultaneous levels of FSH above 40 U/L and estradiol below 30 mg/L is confirmatory).

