29	672:00	8:00		ambulatory visit	X	X	X		X	X	X ⁵
36	840:00	8:00		ambulatory visit	X						X
43	1008:00	8:00		ambulatory visit	X	X					X
57	1344:00	8:00		ambulatory visit	X	X					X ⁵
71	1680:00	8:00		ambulatory visit	X	X					X
92 ±2	2184:00	8:00		ambulatory visit	X	X	X ¹⁴				X
120 ±3	2856:00	8:00		ambulatory visit	X	X					X
148 ±3	3528:00	8:00		ambulatory visit	X	X					X
3	176 ±3	4200:00	8:00	EoTrial ¹²	X	X	X ¹⁴	X	X	X	X ⁵

Proprietary confidential information © 2021 Boehringer Ingelheim International GmbH or one or more of its affiliated companies

1. Screening with subject information, informed consent as the first measure, includes physical examination, check of vital signs including temperature, respiratory rate (RR), systolic and diastolic blood pressure (BP) and pulse rate (PR), 12-lead electrocardiogram (ECG), safety laboratory parameters (under fasting conditions), pregnancy test, drug screening, alcohol breath test, demographics (including determination of body height and weight, smoking and alcohol history), relevant medical history, concomitant therapy and review of inclusion/exclusion criteria.
2. The time is approximate; procedures are to be performed and completed within three hours prior to drug administration. Within three hours prior to the planned dosing, planned time -2:00 will be used.
3. Safety laboratory parameters include clinical chemistry, haematology, coagulation and urinalysis; in addition at screening: serology (hepatitis B virus [HBV], hepatitis C virus [HCV], human immunodeficiency virus [HIV], tuberculosis (QuantiFERON TB test), Follicle-stimulating hormone (FSH) and estradiol evaluation in questionable cases for determining postmenopausal status), and drug screening.
4. PK sampling times may be adapted based on information obtained during trial conduct.
5. Standardised assessment of local tolerability using the criteria swelling, induration, heat, redness, pain or other findings.
6. If several actions are indicated at the same time point, the intake of meals will be the last action.
7. Confirmation of fitness includes physical examination.
8. ADAs will be taken at baseline, Day 15, Day 29, Day 43, Day 57, Day 71, Day 92, Day 120, Day 148 and Day 176.
9. Only drug screening and alcohol breath test.
10. Evaluate vital signs at baseline, 10 minutes after and 1 hour post infusion/injection and in case of suspicion of hypersensitivity reaction including anaphylactic reaction.

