3. Only test at screening if total protein is abnormal and it is deemed clinically necessary by the investigator
4. Only if erythrocytes, leukocytes, nitrite or protein are abnormal in urinalysis and it is deemed clinically necessary by the investigator

The tests listed in Table 5.2.3: 2 are exclusionary laboratory tests which may be repeated as required. The results will not be entered in the CRF/database and will not be reported in the CTR. Except for pregnancy test, it is planned to perform these tests during screening only. Drug screening will be performed at screening. Pregnancy testing in women will be performed at screening, prior to treatment on Day 92, and as part of the EoTrial examination.

Table 5.2.3: 2 **Exclusionary laboratory tests**

Functional lab group	Test name
Drug screening (urine)	Amphetamine/MDA Benzodiazepine Cannabis Cocaine Opiates
Infectious screening (blood) ¹	Hepatitis B surface antigen (HBsAg, qualitative) Hepatitis B core antibody (Anti-HBs, qualitative) Hepatitis C antibodies (Anti-HCV, qualitative) HIV antibody (Anti-HIV, qualitative) QuantiFERON (qualitative)
Pregnancy test (Urine)	Beta human chorionic gonadotropin (beta-HCG)
Determining Postmenopausal status(blood)	FSH test (quantitative) Estradiol test (quantitative)

1. Only at screening

Proprietary confidential information © 2021 Boehringer Ingelheim International GmbH or one or more of its affiliated companies

To encourage compliance with alcoholic restrictions, a breath alcohol test will be performed at screening, and may be repeated at any time during the trial at the discretion of an investigator or designate. The results will not be included in the CTR.

The laboratory tests listed in [Tables 5.2.3: 1](#) and [5.2.3: 2](#) will be performed by the local laboratory of the trial site or/and at a clinical research organization designated by the sponsor.

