7.7 DETERMINATION OF SAMPLE SIZE

It is planned to include up to 60 subjects in this trial in order to have in total 50 PK evaluable subjects, 10 subjects per dose group. Up to 10 subjects might be replaced due to early termination. The planned sample size is not based on a power calculation. The size of 10 subjects per dose group is commonly used in single dose studies of the present type and in general considered as sufficient for the exploratory evaluation of single dose safety and PK.

8. INFORMED CONSENT, TRIAL RECORDS, DATA PROTECTION, PUBLICATION POLICY, AND ADMINISTRATIVE STRUCTURE

The trial will be carried out in compliance with the protocol, the principles laid down in the Declaration of Helsinki, in accordance with the ICH Harmonised Tripartite Guideline for Good Clinical Practice (GCP) and relevant BI SOPs.

Standard medical care (prophylactic, diagnostic, and therapeutic procedures) remains the responsibility of the subject's treating physician.

The investigator should inform the sponsor immediately of any urgent safety measures taken to protect the trial subjects against any immediate hazard, and also of any serious breaches of the protocol or of ICH GCP.

The BI transparency and publication policy can be found on the following web page: trials.boehringer-ingelheim.com. The rights of the investigator and of the sponsor with regard to publication of the results of this trial are described in the investigator contract. As a general rule, no trial results should be published prior to finalisation of the CTR.

The certificate of the insurance cover is made available to the investigator and the subjects, and is stored in the ISF.

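### Inclusion 6 prints the estradiol limit as 30 mg/L, a level no woman reaches, so hormone confirmation of menopause in questionable cases rests on FSH alone

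*Protocol*

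**What the plan says.** Inclusion 6 (Protocol Section 3.3.2) lists several ways in which a woman can qualify. One is use of highly effective contraception by women of childbearing potential; another is being postmenopausal. The main definition of the second is clinical: "Postmenopausal, defined as at least one year of spontaneous amenorrhoea". Hormones come in only as a back-up, namely "in questionable cases a blood sample with simultaneous levels of FSH above 40 U/L" together with estradiol under the stated limit. The full pair of limits reads "levels of FSH above 40 U/L and estradiol below 30 mg/L is confirmatory".

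Footnote 3 of both flow charts schedules the tests at screening, for "estradiol evaluation in questionable cases for determining postmenopausal status". Table 5.2.3: 2 lists FSH and estradiol as quantitative blood tests. Neither place gives a unit or a cut-off, and nothing else in the protocol or SAP does. Inclusion 6 is therefore the only place in the documents where the estradiol limit is set.

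**The concern.** A two-hormone rule is useful only if each hormone can change the answer. The unit printed for estradiol is on a scale that looks far from anything a laboratory would report, which raises the question whether that condition can ever fail.

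The number is an operative eligibility threshold. Section 8.3.1 requires documented evidence that each inclusion criterion is met before a subject is allocated, and Section 7.3 counts the inclusion criteria among the adherence checks. A site that follows the text has no working estradiol check. A site that silently substitutes another unit departs from the written criterion.

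Contraception is at stake. The postmenopausal route is an alternative to the contraception route in inclusion 6, and Section 4.2.2.2 requires contraception during the trial only of women of childbearing potential. A woman wrongly confirmed as postmenopausal would not be held to it, although the drug has a residual effect period of 16 weeks (Section 1.2.6).

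**Working it through.** The limit is stated, not derived from other figures, so there is no calculation in the plan to reproduce. The check is a unit conversion and a comparison.

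Inputs from the protocol:
- Estradiol limit: below 30 mg/L (Section 3.3.2, inclusion 6).
- FSH limit: above 40 U/L in the same sample (same place).
- Age at entry: 18 to 45 years (inclusion 3).

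Input assumed, because the documents give no estradiol range: about 10 to 1,000 pg/mL outside pregnancy, and 50,000 pg/mL as a generous upper bound that covers pregnancy.

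Step 1, conversion. 1 mg/L = 1,000,000 ng/L, and 1 ng/L = 1 pg/mL. So 30 mg/L = 30 × 1,000,000 = 30,000,000 pg/mL.

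Step 2, ratio of the printed limit to the assumed values:

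| Estradiol (assumed), pg/mL | Limit ÷ value | Below the limit? |
|---|---|---|
| 10 | 30,000,000 ÷ 10 = 3,000,000 | yes |
| 1,000 | 30,000,000 ÷ 1,000 = 30,000 | yes |
| 50,000 | 30,000,000 ÷ 50,000 = 600 | yes |

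Step 3, effect on the rule. The confirmation requires FSH above 40 U/L and estradiol below the limit. The second condition is true for every value in the range, so the pair gives the same answer as FSH above 40 U/L alone.

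Step 4, sensitivity to the assumed range. The condition would exclude someone only at 30,000,000 pg/mL or more, so the assumed upper bound would have to be too low by a factor of 600 before the conclusion changed.

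Step 5, sensitivity to a misread prefix. The text was read from PDF by a program, so the same numeral was tried in two other units.
- 30 µg/L = 30,000 pg/mL. This is still 30,000 ÷ 1,000 = 30 times the top of the assumed non-pregnant range, so outside pregnancy the condition would still never fail.
- 30 ng/L = 30 pg/mL. This lies inside the assumed range, and the condition would discriminate.

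This step shows only how the finding depends on the prefix. It does not establish which unit was meant.

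**The case against.** The strongest objection is that everything turns on one letter in a machine-read unit, and a reading error cannot be excluded. That stands, and it is why the fix begins with the source document. Step 5 limits it: not every misreading would remove the problem.

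The second objection is that the limit plays a small part, and this also stands. Postmenopausal status is defined by amenorrhoea, and the hormones only confirm it, in questionable cases, within one of several routes in inclusion 6. FSH still has to exceed 40 U/L. Inclusion 1 requires the investigator to judge the subject healthy, exclusion 6 covers hormonal disorders, and exclusion 22 lets the investigator refuse an unsuitable subject. The flow charts mark pregnancy tests at screening, Day 1, Day 92 and Day 176. The first two precede the single dose, and exclusion 24 bars a woman with a positive test. What remains is conception after dosing: later tests can detect that but not prevent it, and none is scheduled between Day 1 and Day 92.

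Third, laboratory staff might notice an impossible unit and query it. That is plausible, but the documents do not provide for it.

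A reader might also infer that at least 15 women are affected, from three women in each of five groups (3 × 5 = 15). The documents do not support that: 15 is the minimum number of women in 50 subjects, not the number of questionable postmenopausal cases, which is unknown and could be zero.

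**Conclusion.** As printed, the estradiol limit is wrong: it lies at least 600 times above any value in the assumed range, so the two-hormone confirmation reduces to FSH above 40 U/L plus the amenorrhoea history. This rests on the assumed range, with a very wide margin, and on the unit having been read correctly.

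The reach is narrow. Probably very few women aged 18 to 45 would use this route, and the other eligibility criteria and pregnancy tests remain in force. The residual risk is a woman of childbearing potential wrongly confirmed as postmenopausal and so released from the contraception requirement.

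Two stronger readings should be set aside. One is that entry of women in general is left unguarded; the limit is only a confirmatory step within one route. The other is that trial results are compromised. The primary endpoints, the analysis sets and the dose-proportionality model do not use this limit. The sample size does not depend on it either: "The planned sample size is not based on a power calculation". It merits correction as an eligibility safeguard, not as a threat to the analysis.

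**What to change.** First check the unit in the source document. If it reads mg/L, the sponsor should confirm the intended unit and limit, correct inclusion 6 so that the limit falls within the reporting range of the site laboratory's assay, and notify the site. No cut-off is proposed here; that is for the sponsor to state.

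Table 5.2.3: 2 needs no change, since it lists test names without units. The cost is one unit in the next amendment and a note to the site. No extra sample or test is needed, because estradiol is already measured quantitatively when the question arises.

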3.3.3 Exclusion criteria

Subjects will be excluded in the trial if they meet the following criteria:

1. Major surgery (major according to the investigator's assessment) performed within 12 weeks prior to treatment or planned within 12 months after screening, e.g. hip replacement.
2. Any finding in the medical examination (including BP, PR, RR, Body temperature or 12-lead ECG) deviating from normal and assessed as clinically relevant by the investigator.
3. Repeated measurement of systolic BP outside the range of 90 to 140 mmHg, diastolic BP outside the range of 50 to 90 mmHg, or PR outside the range of 50 to 90 bpm.
4. Any laboratory value outside the reference range that the investigator considers to be of clinical relevance.
5. Any evidence of a concomitant disease assessed as clinically relevant by the investigator.
6. Gastrointestinal, hepatic, renal, respiratory, cardiovascular, metabolic, immunological or hormonal disorders. Diseases of the central nervous system (including but not limited to any kind of seizures or stroke), and other relevant neurological or psychiatric disorders.
7. History of relevant orthostatic hypotension, fainting spells, or blackouts.
8. Chronic or relevant acute infections including active and latent tuberculosis, human immunodeficiency virus (HIV) or viral hepatitis; QuantiFERON TB test will be performed at screening.
9. History of allergy/hypersensitivity to the systemically administered trial medication agent or its excipients.
10. Use of any Chinese traditional medicines and drugs (including prescription drug or over the counter) within 30 days of planned administration of trial medication.
11. Subject has been treated with any investigational drug of chemical or biologic nature within a minimum of 60 days or five $t_{1/2}$ (whichever is longer) of the drug prior to the Baseline (Week 0) Visit, or concurrent participation in another clinical trial in which investigational drug is administered.
12. Administered live vaccine within six weeks prior to treatment or have plans for administration of live vaccines during the trial period.
13. Smoker (more than ten cigarettes or three cigars or three pipes/day).
14. Inability to refrain from smoking on specified trial days.
15. Alcohol abuse (consumption of more than 20 g/day for females and 30 g/day for males).
16. Drug abuse or positive drug screening.
17. Blood donation of more than 100 mL within 30 days prior to administration of trial medication or intended blood donation during the trial.
18. Intention to perform excessive physical activities within one week prior to the administration of trial medication or during the trial.
19. Inability to comply with the dietary regimen of the trial site.
20. A marked baseline prolongation of QT/QTc interval (such as QTc intervals that are repeatedly greater than 450 ms in male or repeatedly greater than 470 ms in females) or any other relevant 12-lead ECG finding at screening.
21. A history of additional risk factors for *Torsade de Pointes* (such as heart failure, hypokalaemia, or family history of Long QT Syndrome).
22. Subject is assessed as unsuitable for inclusion by the investigator, for instance, because the subject is not considered able to understand and comply with trial requirements, or has a condition that would not allow safe participation in the trial.

Proprietary confidential information © 2021 Boehringer Ingelheim International GmbH or one or more of its affiliated companies

23. Any documented active or suspected malignancy or history of malignancy within 5 years prior to screening, except appropriately treated basal cell carcinoma of the skin, squamous cell carcinoma of the skin or in situ carcinoma of uterine cervix.
24. Female subjects will be excluded in the trial if they meet the following criteria:
 - Positive pregnancy test, pregnancy or plans to become pregnant up to 16 weeks of trial drug administration
 - Lactation

For trial restrictions, refer to [section 4.2.2](#).

3.3.4 Withdrawal of subjects from treatment or assessments

Subjects may discontinue trial treatment or withdraw consent to trial participation as a whole ('withdrawal of consent') with very different implications; please see sections 3.3.4.1 and [3.3.4.2](#).

If a subject is removed from or withdraws from the trial prior to the first administration of trial medication, the data of this subject will not be entered in the case report form (CRF) and will not be reported in the clinical trial report (CTR). If a subject is removed from or withdraws from the trial after the first administration of trial medication, this will be documented and the reason for discontinuation must be recorded in the CRF; in addition, the data will be included in the CRF and will be reported in the CTR.

At the time of discontinuation, a complete EoTrial examination will be performed, if possible, and the information will be recorded in the CRF. If the discontinuation occurs before the end of the REP (see [section 1.2.6](#)), the discontinued subject should if possible be questioned for AEs and concomitant therapies at or after the end of the REP in order to ensure collection of AEs and concomitant therapies throughout the REP, if not contrary to any consent withdrawal of the subject.

If it is known that a subject becomes pregnant during the trial, administration of the trial medication is to be stopped immediately, and the subject is to be removed from the trial. The subject is to be followed until she has given birth or until the end of the pregnancy. The subject's data are to be collected until the end of the trial (last visit of last subject) and reported in the CTR. For the reporting of pregnancy and associated events, refer to [section 5.2.6.2.4](#).

